- Diarrhea / Colitis and intestinal perforation
- Pneumonitis / ILD
- hepatitis / transaminase increases
- Endocrinopathies (i.e. events of hypophysitis/hypopituitarism, thyroiditis, adrenal insufficiency, hyper- and hypothyroidism and type I diabetes mellitus)
- Rash / Dermatitis
- Nephritis / Blood creatinine increases
- Pancreatitis / serum lipase and amylase increases
- Myocarditis
- Myositis / Polymyositis
- Intestinal Perforations
- Other inflammatory responses that are rare/less frequent with a potential immune-mediated etiology include, but are not limited to:
 - Pericarditis
 - Neuromuscular toxicities (such as Guillain-Barre syndrome and myasthenia gravis)
 - Sarcoidosis
 - Uveitis
 - Other events involving the eye and skin
 - Hematological events
 - Rheumatological events
 - Vasculitis
 - Non-infectious meningitis
 - Non-infectious encephalitis.

Clinical Study Protocol
Drug Substance DURVALUMAB/TREMELIMUMAB
Study Number ESR 15-11561-61-DUNE
EudraCT Nº: 2016-002858-20
Edition Number: 5.0 dated on June 09th, 2021

It is possible that events with an inflammatory or immune mediated mechanism could occur in nearly all organs.

In addition, infusion-related reactions and hypersensitivity/anaphylactic reactions with a different underlying pharmacological etiology are also considered AESIs.

Further information on these risks (e.g. presenting symptoms) can be found in the current version of the durvalumab and tremelimumab Investigator Brochure.

Guidelines for the management of patients with immune-related AEs (irAEs) are provided in Appendix 1. In addition to the dose modification guidelines provided in Appendix 1, it is recommended that irAEs are managed according to the general treatment guidelines outlined for ipilimumab (Weber et al, 2012). These guidelines recommend the following:

- Patients should be evaluated to identify any alternative etiology.
- In the absence of a clear alternative etiology, all events of an inflammatory nature should be considered immune related.
- Symptomatic and topical therapy should be considered for low-grade events.
- Systemic corticosteroids should be considered for a persistent low-grade event or for a severe event.
- More potent immunosuppressives should be considered for events not responding to systemic steroids (eg, infliximab or mycophenolate).

If the Investigator has any questions in regards to an AE being an irAE, the Investigator should immediately contact the Study Physician.

Infusion reactions

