	
For patient treated with PDL-1 inhibitors, hold study drug/study regimen until resolution to Grade ≤1; study drug/study regimen can be resumed after completion of steroid taper. Permanently discontinue study drug/study regimen for Grade 3 if toxicity does not improve to Grade ≤1 within 14 days.
 
Permanently discontinue study drug for 1) Grade 3 colitis in patients treated with CTLA-4 inhibitors or 2) Any grade of intestinal perforation in any patient treated with ICI.
	
For Grade 3 or 4
 
 Promptly initiate empiric IV methylprednisolone 1 to 2 mg/kg/day or equivalent. Monitor stool frequency and volume and maintain hydration. 
 Urgent GI consult and imaging and/or colonoscopy as appropriate. If still no improvement within 2 days, continue steroids and promptly add further immunosuppressants (e.g., infliximab at 5 mg/kg IV, may be repeated at 2 and 6 weeks after initial dose at the discretion of the treating provider). Caution: Ensure GI consult to rule out bowel perforation and refer to infliximab label for general guidance before using infliximab. If perforation is suspected, consult a surgeon experienced in abdominal surgery immediately without any delay.
	
Grade 4
 
Permanently discontinue study drug/study regimen.
	

Hepatitis (elevated LFTs)	Any Grade (Refer to NCI CTCAE applicable version in study protocol for defining the CTC grade/severity)	General Guidance	For Any Grade

PLEASE SEE shaded area immediately below this section to find guidance for management of “Hepatitis (elevated LFTs)” in HCC patients
 
Infliximab should not be used for management of immune-related hepatitis.
			
 Monitor and evaluate liver function test: AST, ALT, ALP, and TB. Evaluate for alternative etiologies (e.g., viral hepatitis, disease progression, concomitant medications).
	
Grade 1
 
 No dose modifications. If it worsens, then treat as Grade 2. 		
For Grade 1
 
 Continue LFT monitoring per protocol.

Grade 2

- Hold study drug/study regimen dose until Grade 2 resolution to Grade ≤ 1 .
- If toxicity worsens, then treat as Grade 3 or Grade 4.
- If toxicity improves to Grade ≤ 1 or baseline, resume study drug/study regimen after completion of steroid taper.

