	
Study drug/study regimen can be resumed once patient stabilizes and after completion of steroid taper.
 
Patients with endocrinopathies who may require prolonged or continued steroid replacement (e.g., adrenal insufficiency) can be retreated with study drug/study regimen if the patient is clinically stable as per investigator or treating physician's clinical judgement.
 
If toxicity worsens, then treat based on severity.
	
 – Consult endocrinologist to guide evaluation of endocrine function and, as indicated by suspected endocrinopathy and as clinically indicated, consider pituitary scan. – For all patients with abnormal endocrine work up, except those with isolated hypothyroidism or type 1 DM, and as guided by an endocrinologist, consider short-term corticosteroids (e.g., 1 to 2 mg/kg/day methylprednisolone or IV equivalent) and prompt initiation of treatment with relevant hormone replacement (e.g., hydrocortisone, sex hormones). – Isolated hypothyroidism may be treated with replacement therapy, without study drug/study regimen interruption, and without corticosteroids. – Isolated type 1 diabetes mellitus (DM) may be treated with appropriate diabetic therapy, and without corticosteroids. Only hold study drug/study regimen in setting of hyperglycemia when diagnostic workup is positive for diabetic ketoacidosis. – For patients with normal endocrine workup (laboratory assessment or MRI scans), repeat laboratory assessments/MRI as clinically indicated.

Amylase/Lipase increased	Any Grade (Refer to NCI CTCAE applicable version in study protocol for defining the CTC grade/severity)	General Guidance	For Any Grade
			
 – For modest asymptomatic elevations in serum amylase and lipase, corticosteroid treatment is not indicated as long as there are no other signs or symptoms of pancreatic inflammation. – Assess for signs/symptoms of pancreatitis 
 – Consider appropriate diagnostic testing (e.g., abdominal CT with contrast, MRCP if clinical suspicion of pancreatitis and no radiologic evidence on CT) – If isolated elevation of enzymes without evidence of pancreatitis, continue immunotherapy. Consider other causes of elevated amylase/lipase – If evidence of pancreatitis, manage according to pancreatitis recommendations
Grade 1		No dose modifications.	

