			
 – The prompt diagnosis of immune-mediated peripheral neuromotor syndromes is important, since certain patients may unpredictably experience acute decompensations that can result in substantial morbidity or in the worst case, death. Special care should be taken for certain sentinel symptoms that may predict a more severe outcome, such as prominent dysphagia, rapidly progressive weakness, and signs of respiratory insufficiency or autonomic instability. – Patients should be evaluated to rule out any alternative etiology (e.g., disease progression, infections, metabolic syndromes or medications). It should be noted that the diagnosis of immune-mediated peripheral neuromotor syndromes can be particularly challenging in patients with underlying cancer, due to the multiple potential confounding effects of cancer (and its treatments) throughout the neuraxis. Given the importance of prompt and accurate diagnosis, it is essential to have a low threshold to obtain a neurological consult. – Neurophysiologic diagnostic testing (e.g., electromyogram and nerve conduction investigations, and “repetitive stimulation” if myasthenia is suspected) are routinely indicated upon suspicion of such conditions and may be best facilitated by means of a neurology consultation. – It is important to consider that the use of steroids as the primary treatment of Guillain-Barre is not typically considered effective. Patients requiring treatment should be started with IV IG and followed by plasmapheresis if not responsive to IV IG.

Grade 1	No dose modifications.	For Grade 1
		
– Consider discussing with the study physician, as needed.– Care should be taken to monitor patients for sentinel symptoms of a potential decompensation as described above.– Consult a neurologist.

Grade 2

Hold study drug/study regimen dose until resolution to Grade ≤1.
Permanently discontinue study drug/study regimen if it does not resolve to Grade ≤1 within 30 days or if there are signs of respiratory insufficiency or autonomic instability.

For Grade 2

- Consider discussing with the study physician, as needed.
- Care should be taken to monitor patients for sentinel symptoms of a potential decompensation as described above.
- Consult a neurologist.
 - Sensory neuropathy/neuropathic pain may be managed by appropriate medications (e.g., gabapentin or duloxetine).

MYASTHENIA GRAVIS:

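### Section 10.1.3 offers infliximab for any steroid-refractory immune event, Appendix 1 rules it out for immune-related hepatitis, and no sentence says which text governs

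*Protocol*

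**What the plan says.** Section 10.1.3 lists the adverse events of special interest. They include hepatitis with transaminase increases, hypothyroidism, type 1 diabetes, lipase and amylase increases, and Guillain-Barre syndrome. The section first names the main source: "Guidelines for the management of patients with immune-related AEs (irAEs) are provided in Appendix 1". It then adds a second one: "In addition to the dose modification guidelines provided in Appendix 1, it is recommended that irAEs are managed according to the general treatment guidelines" for ipilimumab. Five bullets summarise that second source. Two concern drug treatment beyond symptomatic care. One says to consider systemic corticosteroids for persistent low-grade or severe events. The other is "More potent immunosuppressives should be considered for events not responding to systemic steroids (eg, infliximab or mycophenolate". Neither bullet names an organ or an exception.

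Section 6.2.1 places toxicity management for immune-mediated reactions in Appendix 1. It then says that management guidance for events of special interest is also found in Section 10.1.3.

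Appendix 1 describes its own content as a recommendation and gives organ-specific rows:

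- Hepatitis: "Infliximab should not be used for management of immune-related hepatitis". The Grade 3 or 4 row repeats this and names mycophenolate as the example of a further immunosuppressant.
- Endocrinopathy: "Isolated hypothyroidism may be treated with replacement therapy, without study drug/study regimen interruption, and without corticosteroids". Isolated type 1 diabetes is treated similarly as regards corticosteroids.
- Amylase or lipase increase: for modest rises without symptoms, "corticosteroid treatment is not indicated as long as there are no other signs or symptoms of pancreatic inflammation".
- Peripheral neuromotor syndromes: "the use of steroids as the primary treatment of Guillain-Barre is not typically considered effective", after which other treatment is named.

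The general considerations at the start of Appendix 1 also say, without a hepatitis exception, that agents such as infliximab should be considered when steroids fail.

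**The concern.** An investigator managing immune-related hepatitis that has not responded to steroids can reach two protocol texts on the same question. Section 10.1.3 offers infliximab as one of two example agents. The hepatitis rows of Appendix 1 rule it out. Since Section 6.2.1 sends sites to both, reading only one is a foreseeable way to use the protocol.

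The first stake is patient safety, because one passage offers a drug that another excludes for the same condition. The second is interpretation. The safety profile is a secondary objective (Section 2.2), and the SAP summarises toxicities by cohort. If sites followed different texts, the summaries would mix two management policies with nothing in the planned tables to separate them.

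**Working it through.** The plan states no figure on this point, so the check is a comparison of the texts in the current protocol edition, followed by what can be said about size.

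**Step 1. The texts side by side**

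| Event | Section 10.1.3, general bullets | Appendix 1, organ-specific row | Relation |
|---|---|---|---|
| Steroid-refractory immune-related hepatitis | Infliximab or mycophenolate may be considered | Infliximab excluded; mycophenolate named | Direct conflict on infliximab; agreement on mycophenolate |
| Isolated hypothyroidism, isolated type 1 diabetes | Systemic steroids to be considered if persistent low-grade or severe | May be treated without corticosteroids | General text lacks a specific qualification |
| Guillain-Barre syndrome | As above | Steroids not typically considered effective as primary treatment; other treatment named | General text lacks a specific qualification |
| Amylase or lipase rise | As above | Steroids not indicated for modest, symptom-free rises without signs of inflammation | Weakest case: the appendix text covers a narrower situation than the bullet |

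**Step 2. Does any sentence settle the hepatitis conflict?** Three places could do so.

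- Section 10.1.3 names Appendix 1 first, but then adds its own list to what it calls the dose modification guidance there. It does not subordinate the list.
- Section 6.2.1 cites both texts and ranks neither.
- Appendix 1 sends readers to its section on other immune-mediated reactions for events without a specific row. That orders the content of the appendix internally. It does not mention Section 10.1.3.

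Both texts have the status of recommendations, so status does not decide the matter either.

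**Step 3. Size.** The quantity needed is the number of patients with immune-related hepatitis that does not respond to steroids. The documents do not give it. Two figures in Section 1.4.2.3 come near it, and neither measures it.

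- ALT/AST alteration of any grade is listed among events in at least 10% of patients on the combination: 0.10 × 126 = 12.6 patients or more. This counts laboratory changes of every grade and cause.
- The table of expected serious reactions to the combination shows autoimmune hepatitis in 5 and hepatitis in 4 of 2068 patients: (5 + 4) / 2068 = 0.44%, and 0.0044 × 126 = 0.55 patients. Adding the three enzyme terms (AST 5, ALT 2, transaminases 2) gives 18 / 2068 = 0.87%, or 1.1 patients. These sums assume that no patient is counted under two terms. The table leaves out non-serious, life-threatening and fatal events, and it does not record response to steroids, so it is neither an upper nor a lower bound.

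**The case against.** The strongest reply is that the list in Section 10.1.3 is not a rival policy. Appendix 1 opens with much the same general rules, including the infliximab sentence without a hepatitis exception, and then refines them by organ. On that reading the bullets restate the opening and the organ rows prevail. Section 1.4.2.1 also directs management of durvalumab's immune-mediated events, hepatitis among them, to Appendix 1. Every treatment bullet is worded as something to consider, and mycophenolate, the other agent in the disputed bullet, is the one that the hepatitis row names.

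Much of this stands. A reader might infer that Section 10.1.3 requires treatment that Appendix 1 forbids, across hepatitis, hypothyroidism, lipase rises and Guillain-Barre syndrome. The documents do not support that. The bullets permit and do not require. Outside hepatitis, the appendix texts are hedged or limited in scope, and they can be read as refining a permissive general rule. It would also go too far to say that treatment depends on the passage read, since Section 10.1.3 itself points to Appendix 1. Nor can anything be said about the full ipilimumab guideline: only the five-bullet summary is visible, and the source may contain organ exceptions.

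The reply does not remove the hepatitis conflict. The ordering of general and specific text is built into Appendix 1, but nothing extends it to Section 10.1.3. The presence of the same general sentence in Appendix 1 means that there is one more place to align.

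**Conclusion.** The point holds in a narrow form. On infliximab for immune-related hepatitis, Section 10.1.3 and the hepatitis rows of Appendix 1 are inconsistent, sites are referred to both, and no sentence says which governs. The endocrine and Guillain-Barre items are secondary: they show that the general steroid bullet lacks qualifications made elsewhere, and a statement of precedence would deal with them. The lipase item adds little.

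The number of patients affected is unknown and probably small. A reader might take the 13 or so patients expected with ALT/AST alteration, or with hypothyroidism at the same 10% threshold, as the number affected. That figure counts patients with an event of any grade. It does not count patients who would be treated differently under the two texts. The judgement that the number is small rests on steroid-refractory immune hepatitis being a subset of all hepatic events, and on the low counts of serious hepatitis in the pooled data, with the limits given above.

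The sponsor should still act, because the matter bears on the safety of individual patients and wording alone can settle it.

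**What to change.** Two changes, with the clinical content decided by the sponsor's medical lead:

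1. Reconcile the infliximab bullet in Section 10.1.3, and the similar sentence in the general considerations of Appendix 1, with the hepatitis rows of Appendix 1, so that all of them say the same thing about infliximab in immune-related hepatitis.
2. Add one sentence to Section 10.1.3 stating which text governs when its general bullets and the organ-specific rows of Appendix 1 differ. This also covers the endocrine and Guillain-Barre mismatches.

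This write-up takes no view on which clinical rule is right. The change is to protocol wording only and leaves the sample size, endpoints and analyses as they are. Since it concerns patient safety, the amendment route in Section 12.4 (submission to the health authorities and ethics committee approval) would apply.

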10.2 Assessment of safety parameters

10.2.1 Assessment of severity

Assessment of severity is one of the responsibilities of the investigator in the evaluation of AEs and SAEs. Severity will be graded according to the NCI CTCAE v4.03.

The determination of severity for all other events not listed in the CTCAE should be made by the investigator based upon medical judgment and the severity categories of Grade 1 to 5 as defined below:

Grade 1 (mild): An event that is usually transient and may require only minimal treatment or therapeutic intervention. The event does not generally interfere with usual activities of daily living.

Grade 2 (moderate): An event that is usually alleviated with additional specific therapeutic intervention. The event interferes with usual activities of daily living, causing discomfort but poses no significant or permanent risk of harm to the subject.

Grade 3 (severe): An event that requires intensive therapeutic intervention. The event interrupts usual activities of daily living, or significantly affects the clinical status of the subject.

Grade 4 (life threatening): An event, and/or its immediate sequelae, that is associated with an imminent risk of death or with physical or mental disabilities that affect or limit the ability of the subject to perform activities of daily living (eating, ambulation, toileting, etc).

Grade 5 (fatal): Death (loss of life) as a result of an event.

It is important to distinguish between serious criteria and severity of an AE. Severity is a measure of intensity whereas seriousness is defined by the criteria in Section 9.2.1. A Grade 3 AE need not necessarily be considered an SAE. For example, a Grade 3 headache that persists for several hours may not meet the regulatory definition of an SAE and would be considered a non serious event, whereas a Grade 2 seizure resulting in a hospital admission would be considered an SAE.

10.2.2 Assessment of relationship

Relationship of adverse events with study drugs will be assessed by investigators based on toxicity profile described for each study drug (see investigator brochure).

10.3 Recording of adverse events and serious adverse events

Adverse events will be recorded in the eCRF using a recognized medical term or diagnosis that accurately reflects the event. Adverse events will be assessed by the investigator for severity, relationship to the investigational product, possible etiologies, and whether the event meets criteria of an SAE and therefore requires immediate notification and not later than 24 h, to the Sponsor.

Clinical Study Protocol
 Drug Substance DURVALUMAB/TREMELIMUMAB
 Study Number ESR 15-11561-61-DUNE
 EudraCT Nº: 2016-002858-20
 Edition Number: 5.0 dated on June 09th, 2021

The following variables will be collected for each AE:

- AE (verbatim)
- The date when the AE started and stopped
- Changes in NCI CTCAE grade and the maximum CTC grade attained
- Whether the AE is serious or not
- Investigator causality rating against durvalumab or tremelimumab (yes or no)
- Action taken with regard to durvalumab + tremelimumab
- Outcome

In addition, the following variables will be collected for SAEs as applicable:

- Date AE met criteria for serious AE
- Date Investigator became aware of serious AE
- AE is serious due to criteria
- Date of hospitalization
- Date of discharge
- Probable cause of death
- Date of death
- Autopsy performed
- Description of AE
- Causality assessment in relation to Study procedure(s)

Events, which are unequivocally due to disease progression, should not be reported as an AE during the study.

10.3.1 Study recording period and follow-up for adverse events and serious adverse events

Adverse events and serious adverse events will be recorded from time of signature of informed consent, throughout the treatment period and including the follow-up period (90 days after the last dose of durvalumab + tremelimumab).

During the course of the study all AEs and SAEs should be proactively followed up for each subject. Every effort should be made to obtain a resolution for all events, even if the events continue after discontinuation/study completion.

If a subject discontinues from treatment for reasons other than disease progression, and therefore continues to have tumor assessments, drug or procedure-related SAEs must be captured until the patient is considered to have confirmed PD and will have no further tumor assessments.

The investigator is responsible for following all SAEs until resolution, until the subject returns to

Clinical Study Protocol
Drug Substance DURVALUMAB/TREMELIMUMAB
Study Number ESR 15-11561-61-DUNE
EudraCT Nº: 2016-002858-20
Edition Number: 5.0 dated on June 09th, 2021

baseline status, or until the condition has stabilized with the expectation that it will remain chronic, even if this extends beyond study participation.

Follow-up of unresolved adverse events

Any AEs that are unresolved at the subject's last visit in the study are followed up by the investigator for as long as medically indicated, but without further recording in the eCRF. After 90 days, only subjects with ongoing investigational product-related SAEs will continue to be followed for safety.

The sponsor and [REDACTED] retain the right to request additional information for any subject with ongoing AE(s)/SAE(s) at the end of the study, if judged necessary.

Post study events

After the subject has been permanently withdrawn from the study, there is no obligation for the investigator to actively report information on new AE or SAEs occurring in former study subjects after the 90-day safety follow-up period for patients treated with durvalumab + tremelimumab. However, if an investigator learns of any SAEs, including death, at any time after the subject has been permanently withdrawn from study, and he/she considers there is a reasonable possibility that the event is related to study treatment, the investigator should notify the study sponsor, who will inform [REDACTED] Drug Safety.

